## LRTI Initial Antibiotic Use Algorithm

The second arm will be standard care.

Physicians and patients will not be blinded to test type. Tests will be performed on a real-time basis in the ED. All results will be delivered via standard of care through the EMR.

For each of these groups, data of the frequency and duration of antibiotic administration, antiviral use, adherence to evidence based guidelines for treatment of influenza, disposition, concomitant diagnoses, isolation, hospitalizations, and unscheduled return visits or readmissions within a 30 day period will be collected and compared. In addition, we will compare procalcitonin levels for patients diagnosed with RSV or influenza by the Roche LIAT in the test arm compared to those found to have evidence of bacterial infection based on chest xray, blood culture, and other ancillary tests. Where not recommended, reason for antibiotic use will be documented by the pharmacist and abstracted from chart review.

Research coordinators will contact patients and/or parents at 1 and 4 weeks after enrollment for self-reported secondary outcomes including symptom resolution, return to school/work, and follow up healthcare visits, medication adherence (to antibiotics and/or antivirals), and adverse events.

## **G. Data Management and Confidentiality**

All members of the researcher team will be trained in the ED EMR and HIPAA according to IRB and hospital policy. All records will be stored on a password protected computer or UCD encrypted shared drive, or locked in a file cabinet, accessible only to researchers. All data will be coded and the linking code will be kept separate from the main data analysis file.

## **H. Withdrawal of Subjects**

Subjects may be withdrawn from the study without their consent if:

- Their treating physician feels it is no longer prudent for the patient to participate in the study.

## **I. Risks and Side Effects**

For the primary subjects we will be using identifiable protected health information, therefore there are inherent possible confidentiality risks. However, all identifiable data is accessible only to trained users and clinicians who have passwords to the EMR system. Any confidentiality risks are minimal. Identifiable information will be stored in a password-protected database,

where patients will be assigned code numbers. Medical information will be stored in a separate password-protected database, sorted by code numbers. At the completion of the data analysis all identifiers will be erased from the records.

In addition, we plan to analyze aggregate clinical practice patterns through structured data forms. No identifiable data on the clinician will be recorded on research forms. No information on staff members will be recorded, thus we expect no risk to clinician or staff members' employment.

This study also presents several possible physical risks to the subjects randomized to Arm 1 of this study. Risks related to venipuncture for those who consent to an extra needle stick include pain, bruising, bleeding, or infection at the blood drawing site. The total volume of blood obtained for this study in the ED will not exceed 1 mL.

#### **J. Benefits**

This study may benefit the general public by improving clinical diagnosis and management of influenza.

#### **K. Provisions to Protect the Privacy Interests of Subjects**

Patients being considered for enrollment into this study will be approached in their ED rooms to assess their interest and willingness to participate in this study. Patients may request that those present step outside or remain in the room during the informed consent process and discussion.

#### **L. Costs To Subjects**

Procalcitonin testing will be provided at no cost to the subjects and funded by Roche. Patients will not be charged for the procalcitonin testing and it will not be submitted for insurance reimbursement.

#### **M. Subject Compensation**

Subjects will receive a \$10 gift card for their participation in the study.

#### **N. Facilities and Equipment**

Drs. [name] and [name] are both graduates of NIH-supported clinical research training programs (e.g., K30, K12/KL2) with extensive experience conducting clinically-oriented translational research and emerging national reputations in their respective areas. We collectively feel that clinical outcomes studies are an essential and much needed step to demonstrate the real value and impact of molecular testing. [name] was recruited specifically to UC Davis to direct the first ED based antibiotic stewardship program in the nation to our knowledge and will leverage her expertise in translating rapid molecular diagnostic testing to improve clinical outcomes in the ED setting. UC Davis is also an up-and-coming research institution nationally and the UC Davis Department of Emergency Medicine is among the most highly respected academic and research-oriented emergency departments in the United States. The pediatric ED is a member of the national Pediatric Emergency Care and Research Network, which has been funded by NIH for many years and participated in numerous pediatric clinical trials including a focus on infectious diseases. The UC Davis Department of Emergency Medicine is well suited for this project, having demonstrated broad and sustained growth in its research program and productivity over the past decade. The Department demonstrates its support for research with a robust research

infrastructure, which includes a Vice Chair for Research, two Research Managers (one focused on multicenter research), and four full-time clinical research coordinators.

#### **Q. Devices**

I confirm that all investigational devices will be labelled in accordance with FDA regulations and stored and dispensed in such a manner that they will be used only on subjects and be used only by authorized investigators.

#### **P. Statistical Analysis**

We will use standard descriptive statistics to summarize patient characteristics at randomization; mean and standard deviation (SD) for continuous variables and frequency and proportion for categorical variables. We will indicate the count of missing data for each variable. For the comparison of the primary outcomes, we will use frequency and proportions by arm, and compute a point estimate for the difference along with 95% confidence interval (CI) and p-value. We will stratify analysis based on flu status. For primary analyses (unstratified), we will use a Chi-square test (and Fisher exact test), and for stratified analyses, we used Mantel-Haenszel method. Secondary outcomes will be performed similarly. Statisticians and other investigators will remain blinded to treatment identity (e.g., data analyses with A/B coding). For all analyses, we will use SAS 9.4 (SAS Institute, Cary, NC).

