### **A. Objective**

Roche Cobas Liat Flu/RSV POC Assay and procalcitonin testing as part of a stewardship intervention optimizes antiviral treatment and reduces antibiotic treatment for ED patients (under 50 years of age) with suspected influenza or RSV v. standard care using a prospective, patient-randomized design. In addition to the primary outcome, we will evaluate secondary outcomes including aggregate physician adherence to CDC guidelines for the treatment of influenza, antibiotic duration, hospital admission, and emergency department (ED) return visits within 30 days for patients diagnosed with influenza and RSV. Additional secondary outcomes would include time to resolution of symptoms, return to school/work, and subsequent healthcare utilization (e.g. doctor visits) obtained through patient self-report.

Hypothesis: The rapid waived POC assay and procalcitonin, as part of a stewardship intervention will lead to reduced antibiotic treatment by 20 percentage points compared to the control group for antibiotic non-responsive conditions including ILI and nonspecific URI and will increase appropriate antiviral treatment of patients with influenza at high risk recommended to receive treatment by 20 percentage points.

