### **C. Study Population**

**Inclusion criteria:** Patients <50 who are evaluated by the clinician for suspected influenza, including symptoms of ILI (fever >38°C and cough or sore throat) or non-specific URI for whom the clinician suspects RSV or influenza or lower respiratory infection (with or without ordering a chest xray).

**Exclusion criteria:** Patients who are pregnant, prisoners, or are unable to give informed consent in English or Spanish. Patients with influenza-like illness and upper respiratory symptoms for whom the provider is unwilling to wait for procalcitonin results.

**Sample size:** We plan to enroll 100 patients in each arm over a 12 month period (influenza season), which will have 80% power to detect a true 20 percentage point reduction in antibiotic use and 20 percentage point increase in adherence to guideline recommendations for antiviral treatment.

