#### **E. Study Endpoints**

[figure not shown]
The primary study endpoint is the determination of whether use of the Roche Liat Flu/RSV Assay and procalcitonin testing, as part of a stewardship intervention optimizes antiviral treatment and reduces antibiotic treatment for ED patients with suspected influenza. The secondary study endpoints are aggregate physician adherence to CDC guidelines for the treatment of influenza, antibiotic duration, hospital admission, ED return visits within 30 days for patients diagnosed with influenza and RSV, time to resolution of symptoms, return to school/work, and subsequent healthcare utilization (e.g. doctor visits) obtained through patient self-report.

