#### **F. Research Design and Methods**

This will be a prospective, patient-oriented, pilot randomized clinical trial to evaluate (in aggregate) both the use of the Flu/RSV Assay, procalcitonin, and the use of pharmacist-led education for providers in the interpretation of these test results. Children and adults <50 years of age who present to the pediatric ED of the UC Davis Medical Center with influenza-like illness (ILI), upper or lower respiratory infection (URI) will be eligible to participate.

Consented patients in the pediatric ED will be randomized into two arms: The intervention arm will receive procalcitonin with a patient specific stewardship intervention during the ED visit. The intervention will be pharmacist-led and include direct delivery to clinicians of information about interpreting test results and recommendations for antiviral-treatment for high-risk patients, and infection control precautions for patients being hospitalized with a positive RSV or influenza test and avoidance of antibiotics where not indicated. Clinician adherence to treatment guidelines with and without the educational intervention will be compared. Patients randomized to this arm will also have 1 ml of blood drawn for procalcitonin (PCT) analysis to identify bacterial infections. This sample will be taken at the time of a blood draw for standard clinical labs, or from an IV if one is in place. If no blood draw is ordered for standard of care and/or no IV is placed, patients will be given the option to consent to an extra needle stick for the purpose of research if both the clinician and patient agree to wait for the test result. Interpretation of the procalcitonin where obtained will be included in the intervention by the ED pharmacist. We will use the following protocol to guide clinicians in recommendations for antibiotic therapy. Procalcitonin will be an adjunct to guiding decision making for antibiotic use and will provide added value for both patients diagnosed with RSV and flu, as well as promote reduced antibiotic use for patients who do not have diagnosed flu or RSV and help guide appropriate treatment for those patients suspected of having LRTI. We will use a conservative protocol in both infants and older children similar to the figure attached but with a cutoff of 0.5 for recommendation of initiation of therapy in patients suspected of having LRTI.

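### Flu status defines the strata, the antiviral hypothesis population and a diagnosed-only endpoint, but the plan does not say how it is assigned in controls; if ascertainment differs by arm, these comparisons can be biased either way

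*Combined protocol and SAP*

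**What the plan says.** Section P (Statistical Analysis) states "We will stratify analysis based on flu status" and uses the Mantel-Haenszel method for it. The primary analyses are separate: "For primary analyses (unstratified), we will use a Chi-square test (and Fisher exact test"). Flu status is not defined.

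Flu status or diagnosis also sets two other populations. The section A hypothesis is that the intervention "will increase appropriate antiviral treatment of patients with influenza at high risk recommended to receive treatment by 20 percentage points". Section E lists "ED return visits within 30 days for patients diagnosed with influenza and RSV" as a secondary endpoint. Section C sizes something worded differently: a "20 percentage point increase in adherence to guideline recommendations for antiviral treatment".

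On who receives the Liat assay, the text points several ways.

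- **Towards the intervention arm only.** Sections A and E make the assay part of the stewardship intervention, and section A compares that with standard care. Section F opens by saying the trial will "evaluate (in aggregate) both the use of the Flu/RSV Assay, procalcitonin, and the use of pharmacist-led education for providers". Its later text speaks of Liat diagnoses in the test arm.
- **Compatible with routine testing in both arms.** Section F's arm description does not name the assay: "The intervention arm will receive procalcitonin with a patient specific stewardship intervention during the ED visit". Section I describes only blood-draw risks as physical risks for Arm 1, and section L names only procalcitonin as a funded test. The waiting exclusion in section C covers patients "for whom the provider is unwilling to wait for procalcitonin results" and is silent on the Liat.
- **Compatible with different tests by arm.** Section F says physicians and patients are not blinded to the type of test.

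The second arm is described only as standard care. No section says how an untested patient is classified.

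**The concern.** A stratum or subgroup is safe in a randomised comparison if it is fixed before randomisation, or at least measured in the same way in both arms. If every intervention patient has a PCR result while control flu status depends on what clinicians suspected, ordered or recorded, the flu-positive groups are no longer alike. One holds all flu patients. The other holds the flu patients who were noticed, perhaps with some who did not have flu.

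Whether a control is noticed is likely to be related to whether that control is treated. The flu-stratified results, the antiviral result among patients with influenza, and the 30-day returns among diagnosed patients could then show a difference, or hide one, with no contribution from the intervention. Section P says secondary outcomes will be analysed similarly, so the undefined variable reaches them as well.

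**Working it through.** **The plan's own figure.** Section C gives 100 per arm and 80% power for a 20-point difference. Baseline rates and alpha are not stated; two-sided 0.05 is assumed. For the least favourable pair, 40% v 60%:

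n = [1.96·√(2·0.5·0.5) + 0.842·√(0.4·0.6 + 0.6·0.4)]² / 0.20² = 97 per arm.

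Power at 100 per arm is 0.81. The figure reproduces when the whole arm is the denominator. With 30 flu patients per arm (assumed), power for 40% v 60% would be 0.34. Section C's sizing therefore fits an all-patient outcome better than the flu-only hypothesis in section A.

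**Inputs for the illustrations.** Section B gives clinical diagnosis about 64% sensitivity and 67% specificity. It gives 31% sensitivity of ILI in adults meeting the CDC criteria for antiviral treatment, and says fewer than 40% of patients recommended treatment receive it (40% used here). Assumed: 30% flu prevalence, antibiotics in 25% of flu and 50% of other patients, and the treatment ratios. All cases take every intervention patient as correctly classified, controls as classified by clinical diagnosis, and no true effect.

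**Antiviral contrast among identified flu patients, no false positives.** Let p = 0.40 be the true treated proportion in both arms, q the proportion of control flu identified, and r the ratio of treatment in identified to missed controls. The treated proportion among identified controls is p·r / (q·r + 1 − q).

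| q | r | Identified controls treated | Apparent effect (points) |
|---|---|---|---|
| 0.64 | 1 | 0.400 | 0 |
| 0.64 | 2 | 0.80/1.64 = 0.488 | -8.8 |
| 0.64 | only identified treated | 0.40/0.64 = 0.625 | -22.5 |
| 0.31 | 2 | 0.80/1.31 = 0.611 | -21.1 |

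At q = 0.31 the last pattern is impossible, since 0.40/0.31 = 1.29.

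**The sign can reverse.** Take 100 controls, 30 with flu, q = 0.64, r = 2 and 67% specificity. There are 19.2 true positives and 70 × 0.33 = 23.1 false positives. If false positives are treated at the missed-case rate of 0.244, the control rate is (19.2·0.488 + 23.1·0.244)/42.3 = 0.355, an apparent effect of +4.5 points. If they are treated like identified cases, it stays at -8.8.

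**Mantel-Haenszel antibiotic difference, 100 per arm.** The intervention arm has 30 flu-positive at 0.25 and 70 flu-negative at 0.50. Sensitivity in controls is 64%. Stratum weights are n₁n₀/(n₁ + n₀).

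| Specificity | Control flu+ (n, rate) | Control flu− (n, rate) | Stratum differences (flu+, flu−; points) | Weights | Pooled (points) |
|---|---|---|---|---|---|
| 100% | 19.2, 0.250 | 80.8, 0.467 | 0, +3.3 | 11.7, 37.5 | +2.5 |
| 85% | 29.7, 0.338 | 70.3, 0.462 | -8.8, +3.8 | 14.9, 35.1 | +0.1 |
| 67% | 42.3, 0.387 | 57.7, 0.453 | -13.7, +4.7 | 17.6, 31.6 | -1.9 |

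**Unstratified antibiotic comparison.** Both arms have 0.3·0.25 + 0.7·0.50 = 0.425, so the bias is 0.

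**The case against.** The strongest reply is that one-arm testing is not established. Section F's arm sentence, the Arm 1 risks in section I and the funding in section L all fit a Liat used routinely in both arms. If every participant has the same assay, the strata are sound and only wording needs repair. This stands: a reader might infer that controls go untested, and the documents do not settle that. They do not settle the opposite either, since sections A and E and parts of section F point to the intervention arm.

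A reader might also infer that the trial's main result is compromised. It is not. The primary analysis is unstratified, and for antibiotic use in all randomised patients flu ascertainment plays no part. The pooled stratified bias is also small: about 2 points, against a 20-point target and a 95% confidence half-width of 1.96·√(2·0.425·0.575/100) = 13.7 points. Section F calls the trial a pilot.

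Nor is the 30-day return comparison confined to diagnosed patients. Section F already plans to collect and compare unscheduled returns and readmissions within 30 days for each arm.

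Finally, the accuracy figures come from the plan's background section. They need not carry over to patients already suspected of influenza, RSV or lower respiratory infection in a pediatric ED. That limits the size of the bias, not its mechanism. Under a different mechanism, suppose controls with flu are tested with probability 0.8 if treated and 0.4 if untreated. The observed control rate is then 0.32/(0.32 + 0.24) = 57.1%, an apparent effect of -17.1 points. With the probabilities reversed it is 0.16/(0.16 + 0.48) = 25.0%, or +15.0 points.

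**Conclusion.** The point holds conditionally and should be fixed. The plan stratifies on, and defines populations by, a variable whose ascertainment in controls it leaves open. If ascertainment differs by arm, the flu-stratified, flu-positive and diagnosed-only comparisons are not protected by randomisation, and neither the direction nor the size of the bias is known. The antiviral contrast is most exposed: in these illustrations the bias can be as large as the 20-point effect sought. The pooled antibiotic result is little affected, though the flu-positive stratum may not be. These sizes rest on assumed prevalence, antibiotic rates and treatment ratios.

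The assurance for the unstratified analysis should not be stretched to guideline adherence. A reader might infer that scoring adherence in all randomised patients removes the problem. Scoring may itself need flu status: a rule based on results brings the difference in ascertainment back, and a rule based on suspicion could count an untreated high-risk patient with a negative Liat as non-adherent. Adherence is also listed as a secondary outcome in sections A and E.

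Confidence is medium, because the answer turns on a fact about testing that the documents do not settle.

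**What to change.** 1. Reconcile sections A, E and F on which arms receive the Liat, and state how flu status is assigned to a patient without a result.
2. If every participant has the same assay, keep the flu strata. If not, replace flu status in the Mantel-Haenszel analysis with a factor recorded before randomisation, such as presenting syndrome (ILI, URI or suspected LRTI). Label flu-status and diagnosed-patient comparisons exploratory, and report the number tested and the type of test by arm. Make the all-randomised 30-day return comparison in section F the main one.
3. For antivirals, report use by arm in all randomised patients, and among those classed as high risk from information recorded before randomisation. Neither denominator should depend on a test result. Treat guideline adherence as secondary, state whether its scoring uses test results, and reconcile the section A hypothesis with the outcome sized in section C.

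If both arms already have the Liat, the cost on testing is a clarifying sentence and aligned wording. Otherwise it is SAP text, an enrolment-form item for syndrome and risk class, and a written adherence rule.

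The downside is that flu-specific results become exploratory and the antiviral contrast is diluted. If a 20-point gain is confined to 30% of patients (assumed), it is 0.30 × 20 = 6 points over the arm. Power at 100 per arm is then about 14% for 40% v 46%, or about 22% for 12% v 18% (0.30 × 40% v 0.30 × 60%, with no other patients treated). Both baselines are assumptions.

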Antiviral under-treatment can be attributed to the poor sensitivity of current rapid diagnostic tools. For one, influenza-like illness (ILI) is defined by the CDC as the presentation of fever (temperature of 100°F [37.8°C] or greater) and cough or sore throat. These non-specific symptoms contribute to the low sensitivity and specificity of clinical diagnosis, which are approximately 64% and 67%, respectively. This sensitivity drops even further for those who meet the CDC criteria of patients at high risk for influenza-related complications. An observational cohort study found that the sensitivity of ILI reached only 31% for adult patients who met the CDC's criteria for antiviral treatment, likely due to these patients' dulled immune response. Thus, sensitivity of clinical diagnosis may be lowest for those who need antiviral treatment the most. Rapid influenza antigen tests are more specific, easy to use, and only take 15 to 30 minutes, but have a low sensitivity comparable to provider diagnosis. Procalcitonin has been demonstrated in multiple clinical trials to provide value in guiding antibiotic use particularly in respiratory infections for both adults and pediatric patients.

**Unfortunately fewer than 40% of patients who are recommended to receive treatment for influenza receive it in the ED. There are a variety of reasons for poor compliance with guidelines, including lack of awareness, poor understanding of the potential severity of influenza, and lack of accurate rapid diagnostic tests.** There is great potential for rapid, accurate PCR-based influenza and RSV testing to increase prompt antiviral treatment in high risk-patients, decrease antibiotic use in virally infected patients, and improve infection control. CLIA waived rapid, accurate testing could guide better diagnosis and management and improve patient outcomes.

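### The primary antibiotic comparison leaves out suspected LRTI, a plausibly prognostic fact knowable before randomisation; the test is valid, but it may give up precision

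*Combined protocol and SAP*

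**What the plan says.** Section P (Statistical Analysis) fixes the primary method: "For primary analyses (unstratified), we will use a Chi-square test (and Fisher exact test". It also promises a difference in proportions with a 95% confidence interval. The one stratifier it names is influenza: "We will stratify analysis based on flu status", by Mantel-Haenszel and apart from the primary analysis. Baseline data appear only descriptively, in the plan to "summarize patient characteristics at randomization". No section names an adjustment covariate or a stratified randomisation.

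Section C (Study Population) makes the clinician's suspicion part of eligibility. Besides ILI, it admits "non-specific URI for whom the clinician suspects RSV or influenza or lower respiratory infection". It sets the size, "We plan to enroll 100 patients in each arm", for 80% power to detect a "20 percentage point reduction in antibiotic use" and a "20 percentage point increase in adherence to guideline recommendations for antiviral treatment".

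Two other sections treat presentation as relevant to antibiotics. Section A (Objective) frames the antibiotic hypothesis around illnesses that antibiotics do not treat, naming ILI and nonspecific URI. Section F (Research Design and Methods) gives suspected LRTI its own procalcitonin-based rule for recommending that antibiotics be started. Section F also places randomisation after consent.

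**The concern.** The trial mixes patients in whom antibiotics are mostly not expected to help with patients in whom they may be considered. If control-arm use differs between these groups, a chance difference between arms in the share of suspected LRTI moves the estimated effect up or down. The unstratified comparison carries that noise. A comparison within presentation groups removes it and still estimates a risk difference.

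The sample size leaves little slack, so some lost precision could matter. The plan already includes a Mantel-Haenszel analysis, but attaches it to flu status rather than to a fact fixed at entry.

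**Working it through.** **1. The plan's own figure.** Inputs from Section C: 100 per arm, 80% power, a 20-point difference. Alpha is not stated for the sample size; two-sided 0.05 is assumed from the 95% interval in Section P. The control antibiotic rate is not stated, so the least favourable pair, 60% v 40%, is used. The same pair reversed serves the antiviral outcome, whose only anchor is the statement in Section B that "fewer than 40% of patients who are recommended to receive treatment for influenza receive it in the ED".

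n per arm = [1.96·√(2·0.5·0.5) + 0.8416·√(0.6·0.4 + 0.4·0.6)]² / 0.20² = (1.3859 + 0.5831)² / 0.04 = 96.9, so 97.

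Power at 100 per arm = Φ[(0.20·√100 − 1.3859) / 0.6928] = Φ(0.886) = 81.2%.

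At 50% v 30%, n is 93 and power is 82.8%. Exact Fisher power at 100 per arm is 78.7% (60% v 40%) and 79.2% (50% v 30%). The stated design therefore reproduces, provided all 100 per arm count.

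**2. What stratifying removes.** Let s be the LRTI share, pL and pU the control-arm use in LRTI and other patients, c and t the overall control and intervention rates, and n = 100 per arm.

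- Unadjusted variance: [c(1−c) + t(1−t)] / n.
- Stratified variance: the same sum computed within each stratum and averaged with weights s and 1−s, divided by n.
- With the same 20-point effect in both strata, the difference between the two is 2·s(1−s)·(pL−pU)² / n.

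The factor 2·s(1−s)/n is the variance of the chance difference in LRTI share between arms. At s = 30% its square root is √(0.42/100) = 6.5 points.

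*Example with a large contrast* (s = 30%, 80% v 30%): c = 0.45, t = 0.25. The unadjusted sum is 0.2475 + 0.1875 = 0.435. The part removed is 2·0.21·0.25 = 0.105, leaving 0.330. The reduction is 0.105/0.435 = 24.1%. SE falls from 0.0660 to 0.0574. Power, Φ(0.20/SE − 1.96), rises from 85.8% to 93.6%.

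*Example with a small contrast* (s = 30%, 60% v 40%): c = 0.46, t = 0.26. The sum is 0.4408 and the part removed is 2·0.21·0.04 = 0.0168, a reduction of 3.8%. Power rises from 85.4% to 86.7%.

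**3. Range.** All shares and rates below are assumptions, because the documents give none.

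| LRTI share | Control use, LRTI v other | Variance cut | Power, unadjusted → stratified |
|---|---|---|---|
| 20% | 50% v 40% | 0.8% | 87.4% → 87.6% |
| 30% | 60% v 40% | 3.8% | 85.4% → 86.7% |
| 30% | 70% v 40% | 8.3% | 84.2% → 87.1% |
| 30% | 70% v 30% | 16.2% | 87.4% → 92.4% |
| 30% | 80% v 30% | 24.1% | 85.8% → 93.6% |
| 50% | 80% v 25% | 32.3% | 83.2% → 94.4% |

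**4. Simulation** (20,000 trials per scenario, 100 per arm). Power of chi-square → Mantel-Haenszel:

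- 30% LRTI, 60% v 40%: 84.4% → 85.7%
- 30% LRTI, 70% v 30%: 86.4% → 91.5%
- 30% LRTI, 80% v 30%: 84.6% → 93.1%
- 50% LRTI, 80% v 25%: 83.2% → 94.2%
- 30% LRTI, 50% v 50% (not prognostic): 83.3% → 82.9%

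Type I error of Mantel-Haenszel was 4.8-5.1% across the scenarios.

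**5. Sensitivity to the constant effect.** If the effect is proportional to control use, with the average still 20 points, the gain shrinks. At s = 30%, 80% v 30%, the variance cut is 14.6% rather than 24.1%, and power goes from 85.8% to 90.7%.

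**The case against.** The strongest reply is that nothing here is wrong. A pre-specified chi-square with a risk difference is valid, matches the basis of the sample size, and reaches 80% in what Section F calls a pilot trial. That stands. A reader might infer that the primary test is biased or underpowered; the reproduction in step 1 does not support that.

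Several further objections stand in whole or part:

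- **Strength of prognosis.** It is tempting to call presentation and age strongly prognostic. The documents support this for presentation only qualitatively (Sections A and F), and for age not at all. The size of the gain is therefore unknown and may be close to nil.
- **Analysis population.** Section A ties the antibiotic hypothesis to ILI and nonspecific URI. If LRTI patients are outside that comparison, LRTI cannot be a stratum in it and the gain disappears.
- **No ready variable.** The wording in Section C can be read as placing suspected LRTI within the URI category, and a patient with fever and cough may also have suspected LRTI. No mutually exclusive field is defined, so the gain is cheap but not free.
- **The antiviral outcome.** Section A limits it to high-risk patients with influenza. Nothing suggests that suspected LRTI is prognostic there.
- **Flu status.** A reader might infer that it is certainly established after randomisation. The documents do not time the assay relative to allocation. What can be said is that flu status depends on testing, and that the plan does not say how it is established under standard care.

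None of this removes the core point: the fact is knowable at entry, and adjusting for it costs essentially nothing if it proves uninformative.

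**Conclusion.** The point holds as a precision recommendation for the antibiotic outcome, and only if suspected-LRTI patients are part of that comparison. Under LRTI shares of 20-50%, control use of 50-80% v 25-40% and a constant 20-point effect, the variance of the risk difference falls by about 1% to about 32%, and power rises by about 0 to 11 points. The upper end needs a gap of 50 points or so in control-arm use. With a 10- to 20-point gap the variance gain is about 1-4%. A proportional effect gives smaller gains than a constant one in the example shown. The unadjusted test remains valid and meets the stated power if every enrolled patient counts.

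**What to change.** 1. Reconcile Section A (antibiotic hypothesis limited to ILI and nonspecific URI) with Section C (LRTI enrolled, trial sized on antibiotic use generally), and state the analysis population for the antibiotic outcome.
2. If LRTI patients are included, record presentation before randomisation as one mutually exclusive field: suspected LRTI, yes or no.
3. In Section P, make a Mantel-Haenszel test and a stratified risk difference with 95% CI on that field the primary antibiotic analysis. Keep the unstratified chi-square as a sensitivity analysis.
4. A broad age group may be added as a second stratum, on the understanding that the documents do not show it to be prognostic.
5. Use the pre-randomisation field, not flu status, as the adjusting stratum. If the flu-status analysis is kept, state how that status is established in the standard-care arm.

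The cost is one extra screening field, a few lines of SAP text and a slightly more complex primary analysis. Mantel-Haenszel and SAS are already in the plan.
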